**** END ****

NOTES

Note 1: All post-transfusion vital signs may not have been recorded. Complete those that are in the medical record.

Note 2: Describe the type of reaction. Following are the possible types of reactions: Febrile non-hemolytic transfusion reaction, allergic skin reaction, acute hemolytic transfusion reaction, delayed hemolytic transfusion reaction, bacterial sepsis, shock, anaphylaxis, cardiac overload, hypotension, shock, transfusion-associated dyspnea (TAD), tachycardia, tachypena (respiratory rate >22/minute, chills, fever, shortness of breath, circulatory overload, back pain, sweating, nausea, vomiting, hyperbilirubinemia, etc.

Note 3: The types of CNS injuries include sub arachnoid hemorrhage, subdural hematoma, closed head injury and stroke. Include only if the injury occurred within seven days prior to the study unit transfusion.

Note 4: If noted in medical records, or if <500 mL urine output in 24 hours or new elevated creatinine of >1.5 mg/dL.

Note 5: Select "yes" if aspiration event was witnessed and documented in the medical record. Select "no" if aspiration was suspected but not witnessed.

Note 6: Greater than 3 drinks on 5 or more days a week for males; greater than 2 drinks on 5 or more days a week for females or if documented in medical record.

Note 7: Chronic creatinine >1.5 mg/dL.

Note 8: Select "yes" if medical record indicates history of CHF or CHF present before transfusion during current admission. Select "Yes" if echocardiogram shows ejection fraction less than 40% or shows diastolic dysfunction or if there is cardiomegaly on chest x-ray.

Note 9: Diabetes can be either type I (insulin-dependent) or type-II (non-insulin-dependent).

Note 10: Select "yes" if MD note indicates presence of DIC or if platelet count <100,000/uL + fibrin degradation products or if platelet count <100,000/uL + fibrinogen concentration <100 mg/dL.

Note 11: Select "yes" if patient has lung infiltrate/s on chest x-ray within 8 hours of admission to the emergency room and has evidence of blunt trauma to the chest noted in medical record or has rib fracture/s or was involved in motor vehicle accident.

Note 12: Select "yes" if within 7 days before transfusion.

Note 13: If medical record indicate any one or more of the following: biopsy proven cirrhosis, portal hypertension, or past episodes of upper GI bleeding attributed to portal hypertension, prior episodes of liver failure/enechalopathy/coma.

Note 14: If patient received any RBC transfusion for drop in hemoglobin or hematocrit, select "yes".

Note 15: Extubation date/time should be recorded when the extubation is performed and note that this time may occur beyond the 24-48 hours after the transfusion. If intubation was performed and extubation did not take place (e.g. patient was discharged to a chronic ventilatory care facility while intubated), record No. If no record exists to determine the date/time of intubation, record NR.

Note 16: Calculate the excess fluids administered by fluids given (oral or intravenous) minus fluid losses (urine, gastric suction, thoracic or abdominal drainaige) in 24 hours prior to the transfusion. Write down the amount of excess fluid in mL.

Note 17: Pre-transfusion bacterial sepsis: If MD or nursing note indicates possibility of sepsis or a diagnosis of sepsis; other manifestations include a focus of infection (e.g. pneumonia, cellulitis, skin lucer, wound infection); manifestations of inflammation (e.g. fever, tachycardia, tachypnea), and shock (BP less than 90 mmHg systolic; sweating, cold clammy skin). Laboratory test may also show positive blood culture.

Note 18: Pre-transfusion shock: MD or nursing note indicating presence of shock. Manifestations include low systolic BP (<90 mmHg), tachycardia, cold clammy skin, distal extremity cyanosis, low urine output, mental confusion or somnolence.

Note 19: Calculate ratio by dividing the percent saturation of oxygen on pulse oxy (SO2) by FiO2 (calculate FiO2 as follows: room air = 0.21; one liter oxygen = 0.23; 2 liters = 0.25; 3 liters = 0.27; 4 liters = 0.3, 5 liters = 0.35; 6 & 7 liters = 0.4; and 8-10 liters = 0.49. Example: If oxygen saturation is 90% on 4 liters of oxygen by face mask, then the ratio is 90/0.3 = 300.

Note 20: PF ratio. Calculate by dividing the pO2 (on arterial blood gases) by FiO2 (flow rate of oxygen in decimel of 1.0, e.g., 40% FiO2 = 0.4). Example: Someone with pO2 of 120 receiving 40% oxygen, the PF ratio is $120 \div 0.4 = 300$.

Note 21: The definition of when the reaction occurred is the earliest time at which one or more of the following events were noted: pO2/FiO2 <300; SO2/FiO2 <315, and pulmonary edema on chest x-ray.

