F4. Review to detect presence or absence of hypoxemia indicative of ARDS: In order to further eliminate the unnecessary detailed record review, a focused review of the transfusion episode will be performed to detect hypoxemia occurring within six hours of completion of transfusion. Medical records will be reviewed for the respiratory status within six hours after the completion of the study unit transfusion to detect the following: Oxygen saturation (SpO2) less than 90% by pulse oxymetry without or with oxygen therapy; ratio of SpO2/FiO2 <315; and ratio of PaO2/FiO2 <300 on arterial blood gas analysis. FiO2 will be calculated for patients receiving oxygen by cannula or mask as follows: 1 liter = 0.21; 2 liters = 0.23; 3 liters = 0.25; 4 liters = 0.35; 6 and 7 liters = 0.45, and 8, 9, and 10 liters = 0.49 (Rice TW 2007).

If hypoxemia is documented, a detailed medical record review will be performed by the record review coordinator. The full extended data form will be completed. A Power Point summary of the major events and timeline will be prepared. The completed extended data forms and summaries will be sent to the Triage MD for further review.

Precise incidence rates for hypoxemia as defined in this manner in hospitalized patients are not available. Most of the data on incidence of acute respiratory failure (ARF) are reported in patients who are treated in the intensive care unit (ICU). For example, Flaatten et al have reported an incidence of ARF of 63% among 832 patients treated in the ICU. In 13,346 ICU admissions, 1,231 (9.2%) patients were found to have acute respiratory failure by Luhr et al. Pettila et al have described an incidence of ARF of 32.5% in 520 ICU patients while Vincent et al found that 32% of the 458 ICU patients had ARF at admission to the ICU and 35% of the 991 ICU patients developed ARF during their stay in ICU. Roupie et al report that 43% of the ICU patients required mechanical ventilation. A combined rate of 16% for ARDS and ALI in 1977 ICU admissions has been observed by Bersten et al. These data show a wide range for ARF in ICU patients. In order to be more conservative in our estimates for the number of charts requiring detailed review, we have estimated that 60% of the study patients would have hypoxemia/acute respiratory failure and would therefore require detailed chart review along with a review by a triage critical care physician (see below).

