A list of the components that were supplied to each participating hospital will then be printed by the blood center and provided to each corresponding transfusion service medical director or designated individual to identify corresponding recipients and to have the radiology and the medical records be abstracted by the record review coordinator(s). All information will be tracked and compiled into the tracking and data management systems either directly by research staff at the blood center/blood bank or by Westat, if forms are mailed to the coordinating center for data entry.

The coordinating center will be responsible for formation of the medical review board. The medical review board will assess all completed data forms in a blinded manner to determine the presence or absence of TRALI as described above. The coordinating center will compile the results of these reviews into the data management system to allow for formation of a database that will be used for analyses. The proposed diagnostic criteria for TRALI are detailed in the next section.

F25. Proposed Diagnostic criteria for TRALI: Using the Canadian Consensus Conference criteria, the medical review board will be responsible for reviewing the completed recipient forms and determining the presence or absence of TRALI (Kleinman et al).

- 1. New hypoxemia must be present and hypoxemia is defined as pO2/FiO2 ratio of <300 within 6 hours of completion of transfusion or venous oxygen saturation (SpO2) of less than 90% on room air; or other clinical evidence of hypoxemia (e.g., cyanosis). Based on the recent report from Rice TW et al., additional criteria to determine hypoxemia representative of ARDS will be included as follows: ratio of SpO2/FiO2 <315; where FiO2 will be calculated for patients receiving oxygen by cannula or mask as follows: 1 liter = 0.21; 2 liters = 0.23; 3 liters = 0.25; 4 liters = 0.3; 5 liters = 0.35; 6 and 7 liters = 0.45, and 8,9, and 10 liters = 0.49 (Rice TW 2007).
- 2. Bilateral infiltrates on frontal chest radiograph (obtained within 24 hours of Completion of transfusion) must be present. There must be absence of left atrial hypertension (i.e., circulatory overload). However, if ALI is diagnosed by the expert panel in the presence of left atrial hypertension, the case may be classified as TRALI/TACO (overlap case).

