The recipient data will be linked and the linking would allow follow up of those transfusion recipients who are believed to have had TRALI discovered by the current research. For follow up, other blood components transfused within 6 hours of onset of TRALI will be identified and the donors of involved units will be investigated for leukocyte antibodies using a standardized investigation protocol. In case of any deaths identified by current research that are believed to be due to TRALI, the blood bank medical staff of the hospital will be notified for donor investigation and reporting the case to the FDA as per local hospital protocol. The only risk involved for the recipient is the possibility of loss of confidentiality of private health information. Safeguards will be taken to prevent the loss of confidentiality. Additionally, a certificate of confidentiality will be obtained (see below).

H6A. Certificate of confidentiality: A certificate of confidentiality from the National Institute of Health will be obtained. With this certificate, the researchers cannot be forced to disclose information that may identify the donor or the recipients even by a court subpoena, in any federal, state, or local civil, criminal, administrative, legislative, or other proceedings. The researchers will resist any demands for information from personnel of the United States Government that is used for auditing or evaluation of federally funded projects or for information that must be disclosed in order to meet the requirements of the federal Food and Drug Administration (FDA). Researchers do not plan to voluntarily disclose information obtained with this research.

I. Inclusion criteria

For blood donors, the inclusion criteria include those with HLA antibodies and some of the donors who do not have antibodies. Not all donors with HLA antibodies may be needed. Among

donors without HLA antibodies, the selection will be based on gender and parity frequencymatching at each REDS-II Center with the antibody positive donors.

For transfusion recipients, inclusion criteria will be all those recipients who received the study blood components at participating hospitals. Further record review will be conducted on those recipients who had a chest x-ray within 24 hours after the study transfusion.

J. Exclusion criteria

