- **2.** Record the date and time which is nearest to the time of study unit transfusion if there is more than one chest X-ray taken within 24 hrs prior and 24 hrs after the study unit transfusion

Appendix G: Extended Data Collection Form LEUKOCYTE ANTIBODIES PREVALENCE STUDY – PHASE II EXTENDED DATA COLLECTION FORM

Please refer to clinical information from daily chart notes, laboratory test results, radiology reports, echocardiogram reports, discharge summary, nursing notes, blood bank issue and transfusion forms and other chart records to complete this form.

SECTION A: GENERAL INFORMATION

DATE:		ABSTRACTED BY	:						
SOURCE O	SOURCE OF INFORMATION: (Check all that apply)								
ELECTRONIC RADIOLOGY REPORTS DATABASE									
ELECTRON	ELECTRONIC MEDICAL RECORDS INCLUDING RADIOLOGY REPORTS								
PAPER MEDICAL RECORDS									
OTHER (SPECIFY)									
BUI #	BUI #								
		ED EVIDENCE THAT INDEX BLOOD RANSFUSED?	YES Stop data collection	NO Continue					

SECTION B: ADMISSION & DISCHARGE

			DATE	Т	IME (Military)		
HOSPITAL	ADMISSION DISCHARGE						
HUSPITAL				(when available)		
ICU	ADMISSIC	ON					
100	DISCHARGE						
DISCHARGE ST	FATUS	ALI	VE DECEASED				
DISCHARGE D codes. Collect onl	IAGNOSIS L y if NOT prev	.ist up viously	to 10 diagnosis and assigneed in Screening For	0 10 diagnosis and assign ICDDESCRIPTIentered in Screening FormDIAGNOSIS			
				1.			
				2.			
			3.				
				4.			
				5.			
				6.			
				7.			
				8.			
				9.			
				10.			

SECTION C: PATIENT DEMOGRAPHICS

AGE					GENDER	MALE	FEMALE
WEIGHT	HT UNIT			HEIGHT	UNIT		
RACE/ETH	w	B	H	A	Other		

SECTION D: TRANSFUSION ADMINISTRATION

DATE OF Tx:			тім	TIME OF Tx:				AM		РМ	
	List BUI numbers of all involved products and their ABO/Rh type (within 6 hours prior to the onset of reaction):										
BUI #	UI # ABO/Rh			#	ABO/	BO/Rh BUI #		ABO/RI)/Rh	
								-			
VITAL SIGNS (See Note 1) BP (mm		BP (mm	Hg) PULSE/MIN		/MIN	R	RESP/MIN		TEMP (degree F)		
BEFORE Tx:											
1/2 HR DURIN	G:										
1 HR DURING	6 :										
2 HR DURING	; :										
AT COMPLETI OF Tx:	ON										
TX REACTION: (Within 6 hrs of completion of unit)		pletion of	YES			-	REPORTED TO BLOOD BANK:		YES 🗌 NO 🗌]
TYPE OF REACTION: (Describe) See Note 2											

SECTION E: HYPOXEMIA EXCLUSION CRITERIA

Concentrate the chart review process around the time window of 24 hours prior and 24 hours after transfusion of study unit. Please complete respiratory status within **six hours** of completion of the transfusion.

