
Estimate FiO2 as follows, if patient is receiving oxygen by nasal cannula or mask.

Room air: 0.21	1 Liter of O2: 0.23	2 Liters of O2: 0.25	3 Liters of O2: 0.27
4 Liters of O2: 0.30	5 Liters of O2: 0.35	6, 7 Liters of O2: 0.40	8, 9, 10 Liters of O2: 0.49

If receiving oxygen therapy with mechanical ventilation, use percent oxygen recorded on the patient's respiratory care data. Review ventilator data to find FiO2 value (eg. 405 oxygen administration equals a FiO2 of 0.4).

RESPIRATORY STATUS	YES	NO	NR
Oxygen saturation (SpO2) less than 90% by pulse oxymetry without oxygen therapy?			
Oxygen saturation (SpO2) less than 90% by pulse oxymetry while receiving oxygen therapy			
Ratio of SpO2/FiO2 <315 (See Note 1)			
Ratio of PaO2/FiO2 <300 (PaO2 = oxygen saturation on arterial blood gas analysis) (See Note 2)			

If answer to **ANY** of the above respiratory status items is **YES** then further chart review is required. If answer to **ALL** of the above respiratory status items is **NO** then stop now and send copy of form to Westat.

NO.	ITEM	YES	NO	NR	START DATE (If applicable)	RESOLVE DATE (If applicable)	NOTES
1	Acute CNS Injury (within 7 days before Tx)				applicable)	applicable)	Note 3
2	Acute renal failure (within 7 days before Tx)						Note 4
3	Aspiration						Note 5
4	Bone marrow stem cell transplant in past 12 months						
5	Burn as an admitting diagnosis (if within 48 hrs before reaction)						
6	Cancer or recent (within 1 month) chemotherapy						
7	Cardiac bypass during current admission (within 48 hrs before reaction)						
8	Cardiac ischemia during current admission (within 7 days before Tx)						
9	Hx of chronic alcohol abuse						Note 6
10	Hx of chronic renal failure						Note 7
11	Congestive heart failure during current admission (within 7 days before Tx)						Note 8
12	Hx of coronary artery disease						
13	Hx of diabetes mellitus						Note 9
14	DIC during current admission (within 7 days before Tx)						Note 10
15	Drug overdose as admitting diagnosis (within 48 hrs before reaction)						
16	Exposure to high altitude as admitting diagnosis (within 48 hrs before reaction)						
17	Heat stroke as admitting diagnosis (within 48 hrs before reaction)						
18	Hemorrhagic shock during current admission (within 48 hrs before reaction)						
19	High INR (>3.0) during current admission (within 7 days before Tx)						
20	Hx of immunosuppression						
21	Just underwent surgery (within 48 hours)						

SECTION F: PATIENT HISTORY & CLINICAL FINDINGS

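### Note 21, the only definition of reaction onset, omits stand-alone SpO2 below 90% and does not require a new, post-exposure event, so the co-transfused-unit list and risk-factor windows can be misdated in some patients

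*Protocol*

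**What the plan says.** Note 21 of the extended data collection form (Appendix G) defines when the reaction occurred as the "earliest time at which one or more of the following events were noted: pO2/FiO2 <300; SO2/FiO2 <315, and pulmonary edema on chest x-ray". I find no other definition of onset in the protocol.

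The hypoxemia criteria are wider:
- F4 screens on "Oxygen saturation (SpO2) less than 90% by pulse oxymetry without or with oxygen therapy; ratio of SpO2/FiO2 <315", as separate items, plus PaO2/FiO2 below 300.
- Appendix G, Section E has its own yes/no item, "Oxygen saturation (SpO2) less than 90% by pulse oxymetry without oxygen therapy", and a second one for patients on oxygen. A yes to any item sends the chart forward.
- F25, item 1 accepts pO2/FiO2 below 300, "venous oxygen saturation (SpO2) of less than 90% on room air; or other clinical evidence of hypoxemia", and SpO2/FiO2 below 315. It requires the hypoxemia to be new.

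Onset is then used elsewhere. Section D of the form lists involved products "within 6 hours prior to the onset of reaction". H6 says that "other blood components transfused within 6 hours of onset of TRALI will be identified" and their donors investigated. Several risk-factor items in Section F look back 48 h from the reaction, Section G looks back 24 h for extubation, and Section O asks for the blood gas closest to the reaction. F25 allows the qualifying x-ray up to 24 h after completion of transfusion.

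**The concern.** A patient can qualify as hypoxemic on a saturation reading that Note 21 does not recognise as an event. If no blood gas qualifies, onset waits for the x-ray. Note 21 also takes the earliest qualifying event without asking whether it is new or follows the start of the study unit. A patient with edema on the pre-transfusion film, or with a low ratio beforehand, can therefore be given an onset that precedes exposure.

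What is at stake is which co-transfused units are listed and whose donors are then tested, and whether risk factors for acute lung injury fall inside their look-back windows. Those risk factors inform the panel's split of TRALI with and without other risk factors.

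**Working it through.** **Inputs.** The FiO2 values come from Note 19: "room air = 0.21; one liter oxygen = 0.23; 2 liters = 0.25; 3 liters = 0.27; 4 liters = 0.3, 5 liters = 0.35", then 0.40 at 6–7 L and 0.49 at 8–10 L. The ratio cut-off is 315 (Note 21, Section E, F25). The look-back is 6 h (Section D, H6) and the x-ray window 24 h (F25).

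**The plan's own figure.** Note 19's example is SpO2 90% on 4 L: 90 / 0.30 = 300, which reproduces.

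**Step 1: does the ratio item cover SpO2 below 90%?** The ratio is below 315 only when SpO2 < 315 × FiO2.

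| Oxygen | FiO2 | 315 × FiO2 | Readings below 90% that do not set onset |
|---|---|---|---|
| Room air | 0.21 | 66.15 | 67–89 |
| 1 L | 0.23 | 72.45 | 73–89 |
| 2 L | 0.25 | 78.75 | 79–89 |
| 3 L | 0.27 | 85.05 | 86–89 |
| 4 L | 0.30 | 94.50 | none |
| 5 L | 0.35 | 110.25 | none |
| 6–7 L | 0.40 | 126.00 | none |
| 8–10 L | 0.49 | 154.35 | none |

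Edge checks: 66/0.21 = 314.3 sets onset and 67/0.21 = 319.0 does not; 72/0.23 = 313.0 does and 73/0.23 = 317.4 does not; 78/0.25 = 312.0 does and 79/0.25 = 316.0 does not; 85/0.27 = 314.8 does and 86/0.27 = 318.5 does not.

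All four ranges pass the Section E screen. Only the room-air range meets F25's own SpO2 item. Patients on 1–3 L reach F25 through another criterion or through other clinical evidence of hypoxemia, which Note 21 also omits.

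The conversion tables in F4, F25 and Appendix G disagree with one another and must be reconciled. The gap ends at the same flow under each: F4 and F25 give 0.21, 0.23 and 0.25 for 1, 2 and 3 L, hence 67–89, 73–89 and 79–89, and no gap at 4 L (0.35 in F4, 0.30 in F25).

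**Step 2: what a late x-ray does.** If onset is dated t hours after completion, the list opens at t − 6. For t = 3 it opens 3 h before completion; for t = 6, at completion; for t = 12, 6 h after; for t = 24, 18 h after. Take a desaturation 1 h after completion and a first x-ray at 12 h. Dated by the desaturation, the list runs from 5 h before completion (1 − 6) to 1 h after. Dated by the x-ray, it runs from 6 h to 12 h after. The two lists do not overlap. A 48 h risk-factor window opens 36 h before completion (12 − 48) instead of 47 h before (1 − 48).

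**Step 3: onset before exposure.** The screening form collects films from the 24 h before the study unit, and review proceeds on new or worsening findings. Edema on a film 24 h beforehand would, read literally, put the list 24 to 30 h before transfusion. The pilot in F6 reports pre-existing edema in four of six tertiary-hospital recipients. Section H, items 8–10 of the form records pre-transfusion saturations and ratios at the same cut-offs.

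**Scale.** The protocol gives no share of affected cases. The G1 pilot found an x-ray within 12 h in 30% of patients and within 24 h in 42%, so (42 − 30)/42 = 29% of those with a film in the window had their first after 12 h. These are transfused patients in general, so the figure shows only that late films are not rare.

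**The case against.** The strongest reply has four parts.

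- **Note 21 is cited only in Section I**, the vital signs after a reaction, which is left blank when no reaction was noted or reported. Its reach into Sections D, F, G and O and H6 is inferred. That is fair, but if Note 21 does not govern those sections, they use onset with no definition at all. One cited rule is needed either way.
- **Onset in a gap patient need not come from a late x-ray.** A blood gas with PaO2 below 63 on room air (300 × 0.21) dates it, as does escalation to 4 L, where any SpO2 up to 94% gives a ratio below 315 (94/0.30 = 313.3). The x-ray may also come early. This stands and narrows the group.
- **Onset before exposure does not create a diagnosis**, because F25 requires new hypoxemia and no pre-existing acute lung injury. This also stands, but those safeguards do not date the event for the unit list or the risk-factor windows.
- **The study unit is not lost.** A reader might infer that a late onset drops it and leaves its donor uninvestigated. The documents do not support that: Section A of both forms records the unit's identifier, H6 concerns the other components, and under F18 and H6 HNA testing of the study donor is triggered by the case, with no onset window.

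A reader might also infer that cases move to the later side of Section L's 6 h split for acute lung injury, or that the primary comparison or power changes. Section L does not tie that split to Note 21. F4 and F25 time hypoxemia from completion of transfusion, and the panel receives the full form and an event timeline.

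**Conclusion.** The point holds in a limited form. Note 21 contradicts the hypoxemia criteria that it should serve: it misses stand-alone SpO2 below 90% from room air to 3 L, and it lacks a condition that the event be new and follow the start of the study unit. Followed as written, it can date onset up to 24 h after completion or before exposure.

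The damage is a wrong list of co-transfused units for donor investigation (Section D, H6) and shifted look-back windows for risk factors (Sections F and G). It affects patients in the gap ranges with no qualifying blood gas, no escalation of oxygen and a late film, and patients with pre-existing edema or low ratios. How many there are cannot be derived from the protocol. This rests on Note 21 governing every use of onset, the only reading that gives those sections a definition. The study unit and its donor, the F25 timing, the primary comparison and the power are not directly affected. It should be corrected, but it does not threaten the main result.

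**What to change.** Reconcile Note 21 with the hypoxemia criteria in Section E and F25. Define onset as the earliest time, at or after the start of the study unit, at which any of those criteria is newly met, and use the x-ray time only if no oxygenation event is timed. Cite this one definition from Sections D, F, G, I and O of Appendix G and from H6. Reconcile the three FiO2 tables at the same time, since the ratio item depends on them.

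The cost is one form note, a few cross-references and a line in coordinator training. The coordinator already reads saturations and their times for Section E, so no new data source is needed.
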